8.2 SAMPLE SIZE DETERMINATION

To conclude non-inferiority of the interactive remote presence condition with $\geq 80\%$ power, Type I error rate of .025, a non-inferiority margin of 0.025, and assuming a common SD of 0.10 (similar to that observed previously), we propose a sample size of 1476. This estimate conservatively assumes 10% attrition based on a two-sample test of non-inferiority difference in means.

The table below presents statistical power to declare non-inferiority between two means, as defined by the alternative hypothesis, assuming a common standard deviation of 0.10, a Type I error rate of 0.025, a sample size per group of 664, the non-inferiority margin (Δ) specified in the row, and the different combinations of intervention means (μ_1, μ_2) specified by the columns. As long as the difference between the two means is less than the assumed non-inferiority margin, the definition of non-inferiority is met and power can be calculated. However, as can be seen by each row of the table, as the difference in intervention means grows, statistical power will decrease.

To illustrate interpretation of the table, if the mean installation accuracy of in-person instruction is 0.90 and the mean installation accuracy of remote instruction is 0.90 (i.e., the two groups achieve equal accuracy), then 664 persons randomized to each group provides 99.5% power to declare non-inferiority of remote instruction to in-person instruction using a Type I error rate of .025, a non-inferiority margin of 0.025, and a common standard deviation of 0.10. Similarly, if the mean installation accuracy of in-person instruction is 0.90 and the mean installation accuracy of remote instruction is 0.89, the two means are not equal but the difference in means ($0.90 - 0.89 = 0.01$) remains less than the declared non-inferiority margin (0.025). Under this scenario, 664 persons randomized to each group provides 78% power to declare non-

inferiority of remote instruction to in-person instruction using a Type I error rate of .025, a non-inferiority margin of 0.025, and a common standard deviation of 0.10.

Table. Statistical Power assuming 664 persons randomized per group (total N = 1476 with conservatively-estimated 10% attrition).

		Combination of mean accuracy scores for intervention groups				
Δ	$\mu_1 = 0.90$ $\mu_2 = 0.90$	$\mu_1 = 0.90$ $\mu_2 = 0.8975$	$\mu_1 = 0.90$ $\mu_2 = 0.895$	$\mu_1 = 0.90$ $\mu_2 = 0.8925$	$\mu_1 = 0.90$ $\mu_2 = 0.8900$	

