8.3 STATISTICAL ANALYSES

Descriptive Statistics and Covariates. Descriptive statistics for participants randomized to each intervention will be summarized for each outcome using measures of central tendency (mean, median, proportion) and variability (variance, standard deviation, range). Several covariates may impact the relation between the intervention and the outcome measures of interest, and they will be similarly summarized descriptively. These include demographics (age, gender, target child birth order, race, ethnicity, SES); study site; type of vehicle; type of child restraint (including forward- vs. rear-facing); and attitudes, beliefs, and behaviors surrounding child restraints. Because parents will be randomized to the interventions, we expect covariates to be balanced across intervention groups. We will assess balance across intervention groups and utilize covariates in the primary analyses if appropriate. We also will estimate interaction effects to determine whether the intervention is more or less effective among particular subgroups that are adequately represented in the sample.

Primary Analyses. We have three specific aims. Specific Aim 1 is to identify how accurate parents are at installing child restraints using instructions from technicians via interactive virtual presence. We expect to find over 90% or greater of restraints are installed correctly in all respects. We also will investigate individual components of installation and expect over 90% of components, across participants, will be installed correctly. 95% confidence intervals for all of these outcomes will be calculated and presented graphically as a Forrest Plot with a reference line set at 0.90. Identical analyses will be conducted for the group randomized to in-person installation.

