Specific Aim 2 will test whether child restraint installation by interactive virtual presence achieves installation accuracy at a rate not inferior to installation with a live technician. Two models will be computed, one with a measure of installation accuracy (proportion of all child restraint installation components performed correctly) as the dependent variable and the other with the dichotomous outcome of correct (100% correct installation across all components) vs. incorrect installation (<100% correct installation) as the dependent variable. Assuming that improvement is reflected by a positive value (that is, a higher post-training value is better), our primary model, based upon installation accuracy, is:

$$H_0: \Delta_{LIVE} - \Delta_{IVP} \geq \delta \text{ vs. } H_A: \Delta_{LIVE} - \Delta_{IVP} < \delta$$

where δ is the non-inferiority margin and IVP stands for interactive virtual presence. We will assume a non-inferiority margin of 0.025 for the primary analysis (see power analysis) and perform Analysis of

Covariance (ANCOVA) to determine if the difference of mean installation accuracy scores between the two groups falls below the non-inferiority margin of 0.025, after adjustment for the baseline measure of installation accuracy and other relevant covariates. Based on previous work, we do not anticipate non-normality of the continuous outcome variable of installation accuracy. However, we will assess normality using graphical techniques (normal probability plot, histograms) prior to analysis and will transform outcomes if appropriate. The one-sided non-inferiority test will be conducted using a Type I error of 0.025.

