Specific Aim 3 will test parent learning and retention, both through measures of installation accuracy (after the intervention, at start of follow-up visit, and after parent re-installation during follow-up visit) and through the brief knowledge questionnaire administered at post and at follow-up. Six models will be computed using strategies identical to those for Aim 2 and predicting the following dependent variables: (a) installation accuracy (proportion of restraint components performed correctly at start of 4-month follow-up visit); (b) dichotomous outcome of correct vs incorrect installation at start of follow-up visit; (c) installation accuracy after parental re-installation during follow-up visit; (d) dichotomous outcome of correct vs incorrect installation after parental re-installation during follow-up visit; (e) knowledge questionnaire during post visit; and (f) knowledge questionnaire during follow-up visit.

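### The primary accuracy score may be transformed after its plots are seen, but the hypothesis, the 0.025 margin and the power exist only on the raw scale, and the plan's own figures imply a ceiling.

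*Combined protocol and SAP*

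**What the plan says.** Section 8.3, Specific Aim 2, takes as its main outcome "installation accuracy (proportion of all child restraint installation components performed correctly) as the dependent variable". The null hypothesis is a live-minus-remote difference of at least δ. ANCOVA is used to "determine if the difference of mean installation accuracy scores between the two groups falls below the non-inferiority margin of 0.025", with a one-sided type I error of 0.025.

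On distribution, the plan states: "Based on previous work, we do not anticipate non-normality of the continuous outcome variable of installation accuracy". It continues: "However, we will assess normality using graphical techniques (normal probability plot, histograms) prior to analysis and will transform outcomes if appropriate".

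Three other statements bear on the point:

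- Section 8.2 sets the sample size in raw proportion units, "assuming a common SD of 0.10 (similar to that observed previously", with means between 0.89 and 0.90.
- Section 8.3, Specific Aim 1: "We expect to find over 90% or greater of restraints are installed correctly in all respects".
- Section 8.3, Specific Aim 3: "Six models will be computed using strategies identical to those for Aim 2". The transformation rule therefore reaches the follow-up accuracy models (a) and (c).

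No section names a transformation, a trigger for using one, a margin for the new scale or a method of back-transformation. None says whether the plots are pooled or shown by arm.

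**The concern.** A non-inferiority margin belongs to one scale. Once the score is transformed, 0.025 has no defined meaning and the stated null hypothesis is no longer the one tested. Converting the margin does not restore it, because a transformed mean depends on the spread and shape of the scores as well as on their raw mean. The scale would also be chosen after outcome data had been viewed. The same data could then give a different verdict, in either direction. In a child-safety trial, the costly direction is to declare remote help non-inferior when the raw deficit has reached the margin.

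**Working it through.** **Inputs.** From section 8.2: margin 0.025, SD 0.10, 664 per arm, live mean 0.90, and stated power of 0.995 at equal means and 0.780 at a difference of 0.01. From section 8.3: one-sided alpha 0.025, and at least 90% of restraints fully correct. Assumed here, because the plan names nothing: beta-distributed scores, and the arcsine square root and the square as example transformations.

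**1. The plan's own power.** Standard error = 0.10 × √(2/664) = 0.00549. Power = Φ((0.025 − d)/0.00549 − 1.96).

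- d = 0: Φ(2.595) = 0.995.
- d = 0.01: Φ(0.773) = 0.780.

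Both agree with section 8.2, and 1328/0.9 gives N = 1476. The raw-scale calculation is sound.

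**2. Does the plan imply a ceiling?** The cap of 1.00 is (1.00 − 0.90)/0.10 = 1 SD above the mean. A normal curve would put 15.9% of scores above 100%. A beta distribution with this mean and SD has skewness −1.6 and 25% of its scores above 0.975. If Aim 1's expectation holds, at least 90% of scores equal exactly 1.00. Either way the normality plots would not look normal.

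**3. What 0.025 becomes on another scale, starting from 0.90.**

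| | Arcsine square root | Square |
|---|---|---|
| Raw margin if 0.025 is kept | 0.90 − sin²(asin√0.90 − 0.025) = 0.0155 | 0.90 − √(0.81 − 0.025) = 0.0140 |
| Converted margin, 0.90 vs 0.875 | asin√0.90 − asin√0.875 = 0.0396 | 0.81 − 0.875² = 0.0444 |

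The conversion also depends on the starting mean. On the arcsine scale, a raw 0.025 equals 0.034 measured down from 0.85 but 0.052 measured down from 0.95.

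**4. Probability of declaring non-inferiority.** Simulation of 40,000 trials per scenario, 664 per arm, unadjusted difference in means, both SDs 0.10.

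| True raw difference | Raw | Arcsine, 0.025 kept | Square, 0.025 kept | Arcsine, converted | Square, converted |
|---|---|---|---|---|---|
| 0 | 0.995 | 0.791 | 0.789 | 0.993 | 0.998 |
| 0.01 | 0.782 | 0.065 | 0.120 | 0.556 | 0.836 |

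At 0.01 with the converted margin, the verdict differs from the raw verdict in 22.6% (arcsine) or 5.4% (square) of trials.

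**5. False non-inferiority at a true raw difference of 0.025, converted margin.**

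| Remote-arm SD | Raw | Arcsine | Square |
|---|---|---|---|
| 0.10 | 0.026 | 0.001 | 0.026 |
| 0.12 (assumed) | 0.026 | 0.034 | 0.066 |
| 0.15 (assumed) | 0.028 | 0.514 | 0.213 |

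The square shows why. The mean of a squared score is mean² + SD². With live at 0.90 and SD 0.10, this is 0.81 + 0.01 = 0.82. With remote at 0.875 and SD 0.15, it is 0.7656 + 0.0225 = 0.7881. The squared-scale difference is 0.0319, well inside the converted margin of 0.0444, although the raw deficit equals the full 0.025.

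**The case against.** The strongest reply is that the raw scale is the default. The plan does not anticipate non-normality, transforms only where appropriate, and may never do so. If most scores equal 1.00, no monotone transformation removes that point mass, so a sensible team might find none suitable. The two ceiling premises also conflict with each other: with 90% of scores at 1.00, an SD of 0.10 needs a mean of at least 0.967, not 0.90. All this limits how surely the clause would be used. It does not supply a margin if it is used, and each premise on its own contradicts the normality statement.

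Second, the large error rates need unequal SDs, whereas section 8.2 assumes a common SD. This stands as a limit on size. At a common SD of 0.10 and a converted margin, false non-inferiority is not inflated (0.1% and 2.6%), and power at equal means is almost unchanged. The loss at a difference of 0.01 and the disagreement between verdicts remain. The 6% and 12% power figures apply only if 0.025 is carried over unchanged, which the plan does not say.

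Third, the plots may be pooled or blinded. That would weaken the worry about selective choice but leave the scale problem.

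Fourth, the simulations above omit baseline adjustment. A separate simulation of the raw ANCOVA with baseline adjustment and about 90% of scores at 1.00 rejected in 2.45% of trials at the null boundary, so the raw-scale test holds its error rate there too.

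**Conclusion.** The concern holds and should be fixed. It is certain that the plan permits a change of scale for which it has no hypothesis, margin or power. How large the effect would be is conditional on the transformation chosen, the treatment of the margin, the beta shape and, for the inflated error rates, an assumed wider remote-arm SD. Under those assumptions, power at a true difference of 0.01 moves from 78% to between 6% and 84%, and false non-inferiority can reach 51%.

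The stated N and power are correct on the raw scale. The dichotomous outcome is unaffected. In Aim 3 the point reaches accuracy models (a) and (c); the knowledge models (e) and (f) have no stated margin on any scale. At 664 per arm, the raw mean difference does not need normally distributed scores, so the transformation gains nothing for the decision.

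**What to change.** Remove the transformation rule from the primary analysis in section 8.3 and state instead:

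> The non-inferiority decision rests on the ANCOVA of the untransformed proportion. Remote is non-inferior if the upper one-sided 97.5% confidence bound for adjusted mean accuracy, live minus remote, is below 0.025. Any transformed analysis is a sensitivity analysis and does not change the conclusion.

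For Aim 2, replace the sentence on non-normality with a statement that a ceiling at 1.00 is expected. For Aim 3 models (a) and (c), carry over only the raw-scale decision text: the 90% expectation concerns technician-assisted installation, so a ceiling at follow-up is not established. Robust standard errors or a bootstrap interval are an optional check.

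The cost is a few sentences, agreed before any outcome data are viewed. No further data are needed, and N = 1476 and the stated power stand.

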6.3 LOST TO FOLLOW-UP

A participant will be considered lost to follow-up if they fail to attend scheduled visits and/or are unable to be contacted by the study site staff.

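### The 4-month outcomes have no missing-data method: separate ANCOVAs leave out those lost and their post-installation scores, which can distort the 0.025-margin comparison in either direction

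*Combined protocol and SAP*

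**What the plan says.** Specific Aim 3 in section 8.3 lists six models, each to be fitted as in Aim 2. Model (a) concerns "installation accuracy (proportion of restraint components performed correctly at start of 4-month follow-up visit", and (c) concerns accuracy after the parent re-installs at that visit. Models (b) and (d) are the dichotomous versions, (e) is knowledge at the post visit and (f) is knowledge at follow-up.

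For accuracy, the Aim 2 strategy is an ANCOVA "after adjustment for the baseline measure of installation accuracy and other relevant covariates". On the margin the plan says "We will assume a non-inferiority margin of 0.025 for the primary analysis", and on the error rate "The one-sided non-inferiority test will be conducted using a Type I error of 0.025". The covariates named under the descriptive statistics in section 8.3 do not include the post-installation score. Section 7.1 has that score collected from both arms right after the first installation.

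On loss, section 6.3 gives only a definition: "A participant will be considered lost to follow-up if they fail to attend scheduled visits". Section 8.2 adds a sample-size allowance: "This estimate conservatively assumes 10% attrition". The document contains no imputation method, repeated-measures model, analysis-set definition or sensitivity analysis for dropout.

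**The concern.** An ANCOVA at a single time point cannot include a participant who has no score at that time. Without a missing-data rule, anyone who misses the 4-month visit drops out of (a) to (d) and (f), even though nearly all of them will have a post-installation inspection. That inspection is informative about the missing value to the extent that the two scores are correlated.

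The comparison is sensitive because the margin is narrow and the standard error small. If parents who did poorly with the remote technician return less often, while loss in the live arm is unrelated to score, the remaining remote participants look better than the arm as a whole, and a false claim of non-inferiority becomes more likely. The reverse pattern would hide a true non-inferiority. Retention is part of the stated objective, which covers learning as well as installation, and Aim 3 stands under the primary analyses in section 8.3.

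**Working it through.** **Inputs from the documents.** SD and total: "assuming a common SD of 0.10 (similar to that observed previously), we propose a sample size of 1476" (section 8.2). Margin 0.025 and one-sided error 0.025 (section 8.3). Attrition 10%, with no figure by arm (section 8.2).

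**Step 1: reproduce the plan's figures.**
- Size: 2 × 664 = 1328, and 1328/0.9 = 1475.6, so 1476 in total and 738 per arm. The 664 per group are therefore the participants left after attrition, and power is computed on completers.
- Standard error: 0.10 × √(2/664) = 0.0055.
- Power at equal means: Φ(0.025/0.0055 − 1.96) = 0.995, matching "664 persons randomized to each group provides 99.5% power". At a true difference of 0.01: Φ(0.015/0.0055 − 1.96) = 0.780. The other table cells also agree.

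**Step 2: what a bias does to the error.** At a true difference of exactly 0.025, a bias b towards the remote arm gives an error of Φ(b/SE − 1.96).
- b = 0.005 (20% of the margin): Φ(0.005/0.0055 − 1.96) = 0.147.
- Such a bias arises, for example, with 10% loss per arm if lost remote participants score 0.10 below their arm's completers and lost live participants 0.05 below theirs: 0.10 × 0.10 − 0.10 × 0.05 = 0.005.

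**Step 3: range over the post-to-follow-up correlation.** Assumptions not in the documents: 9% to 10% loss, random in the live arm; in the remote arm, those lost score 0.08 to 0.11 lower at post. Simulation with 738 per arm (400 runs per setting) gave a completer ANCOVA bias of 0.0022, 0.0045 and 0.0064 for correlations of 0.3, 0.5 and 0.7. With an ANCOVA standard error of 0.0053, the errors are Φ(0.0022/0.0053 − 1.96) = 6.1%, 13.3% and 22.6%. With 0.0055 they are 5.9%, 12.7% and 21.3%. In round figures: 6%, 13% and 22%. A model that also used the post score had a bias of at most 0.0004.

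**Step 4: other loss patterns.** Separate simulation at a true difference of 0.025, with 738 per arm and 3000 to 4000 runs per scenario. Assumed correlations: baseline to post 0.3; post to 4 months 0.6 unless stated. Loss is logistic in the post score and 10% per arm unless stated. The comparison estimate uses the post score of everyone randomised; a dash means it was not run.

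| Loss pattern | Completer bias | Completer error | Error using post score |
|---|---|---|---|
| Random, or equally related to post score in both arms | about 0 | 0.027–0.028 | 0.025–0.027 |
| One rule on the absolute post score in both arms (live 10%, remote 11.6–13.0%) | 0.0006–0.0018 | 0.032–0.054 | – |
| Low scorers lost in remote arm only | 0.004–0.005 | 0.11–0.15 | 0.02–0.03 |
| Same, correlation 0.3 | 0.0017 | 0.052 | 0.025 |
| Low scorers lost in both arms, remote 15%, live 5% | 0.0036 | 0.10 | 0.024 |
| Low scorers lost in remote arm only, remote 15%, live 5% | 0.007 | 0.26 | 0.026 |
| Low scorers lost in live arm only | −0.0036 | 0.003 | 0.021 |

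The Monte Carlo standard error of a 2.5% rate is √(0.025 × 0.975/3000) = 0.003, so the last column is consistent with the nominal level.

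**Step 5: tipping point.** With 10% of the remote arm missing, lowering each missing score by s lowers the arm mean by 0.10 × s. The claim fails when the confidence bound reaches 0.025, so the room is 0.025 − 1.96 × 0.0055 = 0.0142.
- Observed difference zero: s = 0.0142/0.10 = 0.14.
- Remote arm observed 0.005 worse: (0.0142 − 0.005)/0.10 = 0.09.
- Remote arm observed 0.01 worse: (0.0142 − 0.01)/0.10 = 0.04.

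Dividing 0.025 by 0.10 gives 0.25, but that moves only the point estimate to the margin and overstates robustness.

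**The case against.** The strongest reply is that the plan nowhere says it will analyse completers only. The covariate list is left open, and section 10 refers to an IRB protocol for other aspects, which was not available here. That stands: a reader might infer that the sponsor chose a complete-case rule, and the documents do not support that. Completer-only analysis is what a single-time-point ANCOVA produces when nothing else is specified. Adding the post score as a covariate would not bring back those without a 4-month score.

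A reader might also infer that the bias will favour the remote arm. The documents do not support this either. They give one attrition figure, with no loss by arm and no mechanism, and Step 4 includes patterns with almost no bias and one with bias the other way. Section 6.1 has the intervention stop if the remote connection fails, which only the remote arm can experience. This makes unequal loss conceivable but is not evidence of it.

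Finally, the test that section 8.3 calls its primary model is Aim 2, measured immediately after installation. Loss at 4 months hardly touches it, so this point should not be read as undermining that result.

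**Conclusion.** The gap is real and the effect conditional. Five of the six Aim 3 models, all except (e), depend on attendance at 4 months, have no missing-data method, and leave relevant post-visit data unused. With SD 0.10, about 10% loss and a post-to-follow-up correlation of 0.3 to 0.7, the one-sided error for the accuracy outcomes depends on the pattern of loss:

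- random, or equally related to post score in both arms: near 2.5% to 3%;
- low post scorers lost in the remote arm only: about 6% to 22%, from a bias of about 0.002 to 0.006 (the mildest setting tried gave 5%);
- low scorers lost in the live arm only: about 1% or less, at the expense of power.

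Markedly unequal loss between arms can go beyond this range, as the 15% versus 5% row shows. The correlations and loss patterns are assumptions. The error figures apply to (a) and (c), which fit the 0.025 margin. Models (b), (d) and (f) share the gap, but the plan gives them no margin of their own, so no size is claimed for them. The plan should be changed, because a better method needs only data it already collects.

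**What to change.** - **Accuracy, (a) and (c).** Replace the separate ANCOVAs by one mixed model for repeated measures over the three post-baseline inspections (post, start of follow-up, after re-installation). Include baseline accuracy and its interaction with time, site, arm, time and arm-by-time, with an unstructured covariance. Include everyone randomised with any post-baseline inspection, and read the non-inferiority contrast at each follow-up time.
- **Dichotomous outcomes and knowledge, (b), (d) and (f).** Use the post-visit result in the same way, for example by multiple imputation by arm that includes the post score.
- **Sensitivity.** Add one tipping-point analysis that lowers the missing remote-arm scores until the confidence bound reaches 0.025, and report the shift at which this happens.
- **Wording.** State in section 8.3 who enters each follow-up analysis. Leave the Aim 2 test as it is.

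The cost is SAP text and a little more analysis, with no new data. The model relies on loss being explained by the observed scores. The tipping-point analysis is there to show how far the conclusion depends on that.
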